Appendix 1: Study Synopsis

Title of clinical trial	A feasibility, cluster randomised, 16-week, parallel-group pilot study to investigate the feasibility of trial procedures for a larger multicentre comparison of a digital school-based cognitive behavioural resilience/wellbeing-building intervention ('CUES-Ed') targeting emotional and behavioural problems in vulnerable primary school children in whole classes, compared to the usual school curriculum.
Protocol Short Title/Acronym	Building Resilience in Children. The CUES-Ed research project: feasibility study.
Study Phase if not mentioned in title	Feasibility study
Sponsor name	SLaM/KCL
Chief Investigator	[name]
REC number	LRS/DP-21/22-25994
Medical condition or disease under investigation	Emotional and behavioural problems in vulnerable children (scoring at or below borderline/clinical cut-off) receiving the intervention in whole classes
Purpose of clinical trial	To investigate the feasibility of trial procedures
Primary objective	Evaluate trial procedures
Secondary objective (s)	Estimate parameters to determine sample size for a full trial Validate classroom-based outcome measure Standardise teacher adherence rating Validate child quiz
Trial Design	Parallel group cluster RCT
Endpoints	Primary endpoint: post intervention at 16 weeks
Sample Size	We plan to consent 360 children from 10 schools (each with 2 classes)
Summary of eligibility criteria	Inclusion criteria: In Year 4 of a participating school Parental consent/child assent Exclusion criteria: None
Intervention	A cognitive behavioural resilience/wellbeing building intervention, comprising seven modules with 25 learning objectives, delivered weekly to whole classes, on a digital platform, facilitated by teachers

PROTOCOL IDENTIFICATION Amendment number: Original V1 Issue date: 251021 Authors: [name]
Amendment I 010322: Figures for feasibility amended to proportions; proportion of children giving
baseline data added (as logical follow-on from parental consent/child assent rates).

	(Digital CUES-Ed CBT programme, teacher led). The intervention lasts 12 weeks. The delivery window will be 16 weeks to fit school terms. Assessments will be completed at 0, 8 and 16 weeks, within a 1-month window.
Maximum duration of treatment of a Subject	16-weeks
Version and date of protocol amendments	V1 251021

CONTENTS

ITEMS 1-5: ADMINISTRATIVE INFORMATION.....1-2

- 1. Title**
- 2. Trial registration**
- 3. Protocol version**
- 4. Funding**

6.1 Study Background

6.1.1 Context and need for the CUES-Ed intervention

As many as 1 in 8 school aged children will experience a mental health problem, such as anxiety and depression, with many more experiencing significant emotional difficulties which impact on learning, behaviour, social relationships, motivation and increase vulnerability to mental health difficulties in later adolescence and adult life. 75% of adult mental illness is present by the age of 21, and 50% by the age of 15. Worldwide, mental health conditions account for 16% of the global burden of disease and injury in young people (WHO, 2018).

However, according to the Association of School and College Leaders, 65% of head teachers say they struggle to get mental health services for pupils. Additionally, the NSPCC reports that up to 20% of referrals to CAMHS are rejected. Across King's Health Partners, our services are seeing significant rises in demand and these are forecast to grow by 41% between 2018 and 2028.

CUES-Ed was born out of recognition that children need access to effective early intervention to manage these difficulties, build emotional resilience and prevent mental health difficulties escalating. Teaching children independent skills and effective strategies is fundamental to building this resilience and the capacity they need to move into healthy adolescence and adult life.

This is supported by specific feedback from young adolescents taking part in a CBT research trial (Jolley et al., 2018) highlighting that, whilst they valued the CBT intervention, they had been struggling with their difficulties for a long time and would have liked to learn mental health knowledge and coping skills from a much earlier age. We want to reduce stigma and raise awareness of mental health issues for children and young people by starting developmentally appropriate interventions early - normalising emotional experience and expression and providing accessible, cost-effective, evidence-based treatment. Tackling children's wellbeing and mental health within their school setting enables us to have a far greater, non-stigmatising reach and build strong links between health and education.

6.1.2 CUES-Ed intervention

CUES-Ed is an innovative prevention and early intervention programme rooted in evidence-based Cognitive Behaviour Therapy (CBT) and designed by Clinical Psychologists as a result of direct feedback gathered over many years from children we have worked with in Child and Adolescent Mental Health

CUES-Ed is designed for delivery to whole classes of primary-aged children (7-10 years) to ensure they learn useful ways of looking after themselves and their mental health. They are taught by clinical psychologists or CBT therapists to understand when things are not going well and develop life-long skills to help manage any difficulties now and those that might emerge later in adolescence or adulthood. While all children are expected to gain some benefit, vulnerable children within the class are the key target group for change.

Learning about mental health needs to start from an early age for it to be most effective – and we have found a way of engaging children in a creative and interactive way – with exciting, visually strong and recognisable branding and characters that promote mental health in a positive way.

Across eight whole-class sessions, children learn cognitive strategies and simple but effective behavioural techniques through fun hands-on activities that make abstract concepts more concrete and memorable.

We promote flexible and adaptive responses to difficulties, including self-regulation (the ability to monitor and manage thoughts, behaviours and emotions; especially important when things are difficult or when strong emotions take over) and support-seeking - recognising when extra help is needed. These approaches encourage children to learn the skills that can help build their resilience from an early age. The CUES-Ed workbook for children, parent newsletters, weekly home-tasks and digital development reinforce the key concepts at school and home and promote long-term retention of learning.

Feedback on CUES-Ed from teachers:

"This program has been meaningful and with a clear purpose. The impact on the children cannot be underestimated – this program has not been an 'add on', but has really started to change the attitudes of the children."

"All the children have been able to access the course. They have learned strategies and vocabulary to help them. They have become more confident in recognising and talking about their feelings and are applying their strategies in class, the playground and at home."

"[The best thing about CUES-Ed is] knowledge and skills help children in many areas e.g. friendships, learning, attitude, dealing with problems at home and school. Skills will stay with them as they progress helping them to be reflective and emotionally resilient."

6.1.3 Why Cognitive Behaviour Therapy?

CBT is based on the theory that thoughts, feelings, what we do and how our body feels are all connected. If we change one of these then we can alter the others. When we feel worried or distressed we often fall into patterns of thinking and responding which can worsen how we feel.

CBT helps us notice and change these so that we can feel better - with a range of practical strategies that can help us in the here and now. CBT has a good evidence base which has been carefully reviewed by the National Institute for Health and Clinical Excellence (NICE), who provide independent, evidence-based guidance for the NHS on the most effective ways to treat disease and ill health. It is recommended for a wide range of mental health problems in adults, older adults, children and young people.

CBT also provides a comprehensive range of practical strategies that are applicable to a broad and non-clinical population. As such, it is relevant to the whole class setting where ‘one size doesn’t fit all’. Rather than targeting a specific problem, CUES-Ed utilises core CBT techniques and aims to teach children how to manage their current and future wellbeing - by recognising, understanding and problem solving the transdiagnostic cognitive, social, physiological, perceptual, emotional and behavioural vulnerabilities implicated in a range of mental health problems.

6.1.4 Feasibility of the intervention: safety, acceptability and potential helpfulness

CUES-Ed has been delivered in person to over 6000 primary school children in 78 schools to date, primarily across South London – see Appendix 2 for a full list of the schools we have worked with.

Service evaluation (Redfern et al 2019) shows high ratings of acceptability by children and teachers and improvements on whole class mental health knowledge and well-being. Children’s written feedback suggested benefits in emotional literacy, understanding how to look after their mental health, normalising emotional responses to confusing/difficult experiences, and emotion-regulation strategies.

Feedback on CUES-Ed from children:

“I think my mind is a whole lot calmer and I’m much more aware of my thoughts, my feelings and my behaviours. You have inspired me to tell my family and friends about what we have been doing...”

“I never thought there were so many ways to calm down!”

“CUES-Ed has made me understand more about my feelings and also how to handle my emotions when times are tough. I am very grateful for the CUES-Ed team because they have helped me very much.”

Importantly, children identified as more vulnerable consistently show significant improvement following the CUES-Ed programme. Vulnerability was defined as those scoring within a clinical range on self-report measures of wellbeing/distress. The Children’s Outcome Rating Scale (CORS, Duncan, Miller & Sparks, 2003) measures wellbeing/distress across four items, each rated 0 (worst) to 10 (best); clinical cut-off <32. Me and My Feelings (Deighton et al., 2013) comprises 16 items, each rated 0 (best) to 2 (worst), measuring emotional (M&MF-E) and behavioural (M&MF-B) difficulties (M&MF-E, ten items; borderline/clinical cut-off >9; M&MF-B, six items; borderline/clinical cut-off >5).

See table below:

Measure	n	% of cohort	Pre-Mean (SD)	Post-Mean (SD)	p
Wellbeing / distress	227	45%	22.98 (6.68)	26.56 (8.64)	<0.01
Emotional difficulties	144	28%	11.9 (2.45)	9.99 (3.33)	<0.01
Behavioural difficulties	100	20%	7.43 (1.46)	6.04 (2.44)	<0.01

Key: SD=standard deviation

In-service clinic data for over 3,000 children receiving CUES-Ed showed whole class benefits of children being better able to look after themselves, improved emotional literacy and an increased repertoire of coping strategies. Improved general well-being, emotional well-being and behaviour was found for vulnerable children.

We have also collected teacher-rated outcomes using a bespoke questionnaire since 2016. To date 77 teachers have completed this about their whole class before and after the CUES-Ed programme. Teachers were asked to rate the number of children who never, always or sometimes demonstrate certain classroom attitudes and

behaviours. Following CUES-Ed delivery, teachers reported a significant increase in the number of children who:

- Could self-regulate emotion – i.e. could cheer themselves up when they were feeling sad, worried or angry.
- Were able to use a range of problem-solving strategies.
- Were able to explain why they had behaved in a certain way.
- Would keep going and persevere when they are finding work difficult.

They also reported a significant decrease in the number of children whose feelings got in the way of their learning. In addition, after CUES-Ed delivery teachers reported a significant improvement in their own knowledge of strategies to calm children and help them with worries. Teachers reported that difficult behaviours had significantly less impact within the classroom after CUES-Ed delivery.

6.1.5 Digital teacher-led delivery

Expert delivery is not a suitable model for widescale implementation. Most recently, we have designed a digital version of the programme, for teachers to deliver. Piloting has shown acceptability and feasibility of this format.

6.1.6 The proposed study

To inform a future large scale trial, we wish to first ascertain feasibility of trial procedures, refine our measures, and estimate parameters for sample size calculation in a feasibility pilot study.

6.2 Choice of comparators

We will compare CUES-Ed to a waitlist control intervention. The current state of evidence leaves open the question of whether whole class wellbeing interventions can be helpfully delivered at scale in schools. We are not yet at the stage of choosing between interventions, or identifying the helpful or active components, which would indicate an active control. Asking if delivering is better than not delivering will provide helpful information. A waitlist control intervention is therefore an appropriate choice for a large scale trial. This study is a feasibility pilot to inform such a trial, so we will use the same waitlist control condition as we intend to use in the larger study.

7. Trial Objectives

7.1 Trial Objectives

Aims: We plan to test the feasibility of our trial procedures for a subsequent study evaluating the effectiveness of the CUES-Ed intervention, as an adjunct to the usual school curriculum, compared to the usual school curriculum alone, in reducing emotional and behavioural problems in vulnerable Year 4 schoolchildren in England, receiving the intervention as part of a whole class.

Feasibility will be judged as being able to: randomise schools; obtain parental consent for the use of data for research purposes; deliver the intervention adherently; ensure child attendance; complete child and teacher outcomes at scheduled times (0, 8 and 16 weeks), within a one month window for completion at each timepoint (i.e. between 6 and 10 weeks for the 8 week assessment and between 14 and 18 weeks for the 16 week assessment), with retention from baseline to follow-up. Secondary aims will be to estimate parameters for a sample size calculation for the subsequent larger trial, standardise our measures of adherence of teacher delivery, and validate our teacher-rated measure of classroom behaviour and child quiz.

The sample for the study will comprise consenting (n=360) children in ten schools.
Criteria for judging feasibility are as follows:

7.1.1 Randomising schools:

- Randomisation according to allocation without contamination for all ten schools

7.1.2 Parental and child consent:

- ≥ 60% of targeted parents (i.e. parents of children in participating classes) giving informed consent for data use (n=360, from 600)

7.1.3 Adherent delivery:

- Of the ten teachers delivering the intervention, at least eight achieving acceptable adherence ratings for an observed session

7.1.4 Outcome completion:

- ≥80% of children completing outcome measures and giving assent for these to be used for research (n=288, from 360).

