8.1 Design

The design will be a parallel group feasibility cluster RCT with random allocation of schools to one of two arms, in a 1:1 ratio.

The usual school curriculum will be delivered without interference in both conditions, with assessments at baseline (0-weeks), 8-weeks and 16-weeks (post intervention, primary endpoint) and a proposed primary outcome of emotional and behavioural problems for vulnerable children at 16-weeks. Waitlist control participants will be offered the intervention later in the term or the following school year. The intervention will be delivered to whole classes; each school will be two or three form entry, and thus comprise two or three classes. Each class will comprise around thirty children

PROTOCOL IDENTIFICATION Amendment number: Original V1 Issue date: 251021 Authors: [name] Amendment I 010322: Figures for feasibility amended to proportions; proportion of children giving baseline data added (as logical follow-on from parental consent/child assent rates).

Schools will be randomised to classes receiving CUES-Ed, in addition to the usual school curriculum, either now (CUES-Ed) or later (waitlist control, WL). The usual school curriculum is nationally set, with limited scope for variation by school. We will record what is delivered in the usual curriculum, but will not interfere with usual delivery. In particular, as CUES-Ed will not comprise additional hours of teaching, we will record any difference arising in the routine curriculum delivered in intervention and control schools.

Trained research workers will complete assessments with children and teachers at baseline (T0), 8-weeks (T1) and 16-weeks (T2, post therapy), see Figure 1.

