12.1 Primary outcome measures

For the feasibility outcomes the parameters are based upon the following progression criteria:

Criteria	Green (Go)	Amber (Proceed with changes)	Red (Not feasible to proceed)
Randomise schools	10	8	<8
Consent/Baseline data for children from parents	360/600=60%	240/600=40%	<240/600
Child assent	360/600=60%	240/600=40%	<240/600
Children providing baseline data	360/600=60%	240/600=40%	<240/600
Followed up	%80	70%	<70%
Adherence of teachers	%80	70%	<70%
Fidelity of intervention*	%80	70%	<70%

* Fidelity is determined by whether CUES-Ed schools get CUES-Ed and waitlist control schools do not get CUES-Ed between 0-16 weeks

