13.4 Study flow diagram

Figure 1: Design

14. Sample size

We estimate from two classes within 10 schools there will be approximately 600 children and we anticipate that 60% of parents of the children will consent (n=360). We anticipate the key challenge to the success of running the future confirmatory RCT will be to understand the follow up rate. By consenting and collecting baseline data from 360 children we will be able to estimate the follow up rate (assumed to be 80%) with $\pm 4.1\%$.

15: Recruitment

15.1 Schools:

For the feasibility pilot study, we will recruit schools known to the CUES-Ed service, by liaising directly with local authorities and headteachers. Each school will be approached for headteacher consent. Teachers will be approached by their head to discuss participation. However, as the headteacher is also their manager, they will each have a separate meeting with the research team to ensure they have the opportunity to decline participation should they wish to. Heads will agree, as part of their consent on behalf of the school, to teachers being free to decide to participate or otherwise without this compromising their relationship with their school in any way.

15.2 Parents:

Once headteacher and teacher consent is secured, letters will be sent to all parents in the target year group explaining the study and seeking consent to use outcome measures for a research purpose. Parents will receive one telephone follow-up from the school office – they will be asked if they would be willing for the research team to contact them. Parents agreeing to this contact will also be followed up by the

research team. We will also place research team members in playgrounds during drop-off and pick-up times with additional forms for parents to sign.

15.3 Children:

All children will be invited to attend CUES-Ed sessions and complete outcomes, unless parents, or the children themselves request not to participate. This is because it is important that the parental consent process does not result in children feeling excluded or stigmatised. Children will give assent for the use of the measures for research. This will be given as privately as possible, again to avoid any stigma. We will only use data when both parents and children consent.

METHODS: ASSIGNMENT OF INTERVENTIONS

16. Randomisation

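### Protocol sections 7.1.4 and 12.1 set different tests for child assent and completion, so the same counts can pass one section and be Amber, or fall short, in the other

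*Protocol*

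**What the plan says.** Section 7.1 of the protocol lists the criteria for judging feasibility. For parents, 7.1.2 requires at least 60% "giving informed consent for data use (n=360, from 600"). It describes the sample in the same terms: "The sample for the study will comprise consenting (n=360) children in ten schools". Section 7.1.4 then requires "≥80% of children completing outcome measures and giving assent for these to be used for research (n=288, from 360"). Its denominator is therefore the consented children, and it puts assent and completion into one criterion.

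Section 12.1, which holds the primary outcome measures, gives a Green/Amber/Red table. Three rows carry identical cut-offs (Green 360/600, Amber 240/600, Red below 240/600): "Consent/Baseline data for children from parents", child assent, and "Children providing baseline data". A separate follow-up row is set at 80% Green and 70% Amber, with no denominator or time point.

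Section 15.3 states the rule for usable data: "We will only use data when both parents and children consent". The same section says "All children will be invited to attend CUES-Ed sessions and complete outcomes, unless parents, or the children themselves request not to participate", so measures are completed whether or not a parent has agreed to research use.

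Section 14 builds the 600 from two classes in each of ten schools. Section 8.1 says "each school will be two or three form entry, and thus comprise two or three classes".

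**The concern.** The two sections test child assent against different denominators and at different levels: 80% of 360 in one, 60% of 600 in the other. Nothing says which takes precedence. These thresholds are the study's primary outcome and feed the decision on a full trial, so a reader of section 7 and a reader of section 12 could report different verdicts from the same counts.

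The table also leaves open who is counted in the assent row. If that is settled only once the counts are known, the colour of the row becomes a matter of choice.

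**Working it through.** **Inputs.** 600 children targeted and 360 parental consents (7.1.2, section 14); 288 of 360 assenting and completing (7.1.4); Green 360/600 and Amber 240/600 for consent, assent and baseline data (12.1); 80% follow-up (12.1, section 14).

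**The plan's own figures.** 360/600 = 60%, 240/600 = 40% and 288/360 = 80% all reproduce. Section 14's precision also reproduces as a simple binomial: 1.96 × √(0.8 × 0.2 / 360) = 0.0413, or ±4.1 points. That calculation takes 360 children who have both consent and baseline data, which points to counting baseline data among consented children.

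**Same counts, two verdicts.** Count assent and baseline data among consented children, and take Amber to run from 40% to just under 60%.

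| Counts | Section 7.1 | Section 12.1 |
|---|---|---|
| 360 consents; 288 assent and complete | 7.1.2: 360/600 = 60%, met. 7.1.4: 288/360 = 80%, met | Consent 60%, Green. Assent and baseline data 288/600 = 48%, Amber |
| 480 consents; 360 assent and complete | 7.1.2: 480/600 = 80%, met. 7.1.4: 360/480 = 75%, not met | Consent 80%, Green. Assent and baseline data 360/600 = 60%, Green |

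The second line takes the percentage in 7.1.4 as governing, not the count of 288.

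**What Green in 12.1 requires.** With consent exactly at its Green line, assent and baseline data need 360/360 = 100%. At the 80% rate that 7.1.4 accepts, the number of consents C must satisfy 0.8 × C ≥ 360, so C ≥ 450, and 450/600 = 75% of parents.

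**Consent and assent rows alone.** If the assent row is counted over all children, 360 consents and 360 assents need not be the same children, so two Green rows do not by themselves give 360 with both permissions. A baseline-data row defined as having both would give it.

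**Denominator.** Section 8.1 puts a class at around thirty. One three-form school among ten makes the roll about 600 + 30 = 630, and 360/630 = 57%: Green by count, Amber by percentage.

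**The case against.** The best defence is that 7.1.4 is really the follow-up criterion. Its heading concerns outcome completion, it is the only item in 7.1.1 to 7.1.4 that could carry the retention named at the start of 7.1, and 288 of 360 equals both the Green follow-up row and section 14's assumed rate. Read so, the protocol is one chain: 600 targeted, 360 consented with baseline data, 288 followed up. Assent can be withdrawn later (22.4), so assent at the end is not meaningless. This explains the figure, and that part stands. It does not explain the assent wording: the flowchart in 8.2 and the timeline in section 13 place assent at baseline, where 12.1 tests it on 600.

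The defence is also right that 480 consents, or consent at exactly 360, are chosen cases; that requiring 360 at baseline is strict but coherent with section 14; and that Amber means going ahead with changes, not stopping.

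A reader might infer something stronger: that all three rows could be Green with fewer usable children than the Red line of 240. If 60% consent and 60% assent were independent over 600, the overlap would be 0.6 × 0.6 × 600 = 216, and the arithmetic minimum is 360 + 360 − 600 = 120. The documents do not support this. It needs the baseline row to count children without parental consent, whereas sections 9 and 18.1 have those data destroyed unseen, section 14 plans consent and baseline data on the same 360, and the amendment note describes the baseline proportion as following on from consent and assent. Independence is not stated either.

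**Conclusion.** The inconsistency is real and should be fixed. Its size is 80% of 360 against 60% of 600 for child assent: 288 children meet 7.1.4 but stand at 48%, Amber, in 12.1, and 360 of 480 is Green in 12.1 but 75% against the 80% of 7.1.4. This rests on counting assent and baseline data among consented children and on letting the percentage in 7.1.4 govern. If 7.1.4 is meant as follow-up, the remaining conflict is its assent wording, together with the unstated denominator of the assent row.

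The consequence is a verdict between Green and Amber that depends on the section read. In neither worked case does it reach Red. It would also go too far to call the 600 denominator badly wrong: the synopsis plans two classes per school, and ten three-form schools (900 children, 360/900 = 40%) would be an extreme case. The point is only that the plan should say whether the count or the percentage decides.

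**What to change.** State the same criteria in 7.1 and 12.1, with a numerator and denominator for each row:

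1. Parental consent / all children in participating classes, keeping the 60% and 40% cut-offs.
2. Child assent / children with parental consent, with one threshold that agrees in both sections.
3. Baseline data with both consent and assent / all children in participating classes, 60% and 40%.
4. 16-week data / children in row 3, 80% and 70%, with the assent wording taken out of 7.1.4.

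Say that the percentage of the actual roll governs, since 8.1 allows three-form schools, and keep 360 as the planning figure for section 14.

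The cost is protocol wording only. Green may be slightly harder to reach because row 3 uses the joint count. Row 3 is then the binding line: with consent at exactly 60% it still allows no loss between consent and baseline. The sponsor should accept that knowingly when choosing the row 2 threshold.
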